7.1.4 Pharmacokinetics/Biomarkers

7.1.4.1 Pharmacokinetics for Safety Run-in and Randomization Phase

Ibrutinib and venetoclax should be dosed together at the same time with 8 ounces of water and a meal. It is anticipated that steady state will be reached after 1 week of administration of the highest venetoclax dose. Ibrutinib and venetoclax PK samples will be collected at steady state on the PK days as shown in Table 8 at the time points listed in Table 9.

Table 8. Ibrutinib and Venetoclax PK Samples Schedule at the Target Dose

Dosing Schedule	PK Day		
Standard ramp-up	Week 6 Day 1		

Pharmacokinetics of ibrutinib and venetoclax when dosed in combination will be determined at time-points specified in Table 9 below.

Table 9. Pharmacokinetic Sample Schedule for Ibrutinib and Venetoclax or placebo on the PK Days

			Time after ibrutinib and venetoclax dose					
Study Drugs	Pre-dose PK ^a	Dose ^b	1 hour (± 15 min)	2 hour (± 15 min)	4 hour (± 30 min)	6 hour (± 30 min)	8 hour (± 1 h)	
Ibrutinib and Venetoclax or Placebo*	X	X	X	X	X	X	X	

a Predose samples should be collected 30 minutes prior to the administration of ibrutinib and venetoclax or placebo

b Ibrutinib/venetoclax or placebo should be dosed the same time within 30 minutes after completion of the meal. Example:

Predose PK	7:00 am
Breakfast 7:00 t	to 7:30 am
Dose	7:30 am
1 hr PK	8:30 am
2 hr PK	9:30 am
4 hr PK	11:30 am
6 hr PK	1:30 pm
8 hr PK	3:30 pm

^{*} Unscheduled PK sampling schedule based on Medical Monitor request, e.g. dose modification (at least 7 days after dose modification)

Refer to the laboratory binder for instructions on collecting and processing these samples. On the day of the sampling visit, the clinical staff will instruct the subject to not take a dose before arrival at the clinic. Study drug intake will be observed by clinic staff. The actual time (versus requested time) that each sample is drawn must be recorded using a 24-hour format. The same clock should be used for recording the time of dosing. In the event that medical management is needed, use of concomitant medications should be recorded. In the case of ibrutinib or

venetoclax/placebo dose holds or modifications prior to the above time points, please consult with medical monitor to determine the most appropriate time at which to obtain PK blood samples.

For subjects who must start a moderate or strong CYP3A inhibitor while on treatment with ibrutinib or venetoclax, additional PK blood samples for the evaluation of ibrutinib and venetoclax exposure is requested at least one week after the initiation of the concomitant CYP3A inhibitor. PK samples will be collected at the time points described above.

7.1.4.2 Pharmacokinetics Treatment-naive Open-label Arm

Ibrutinib and venetoclax should be dosed together at the same time with 8 ounces of water and a meal. It is anticipated that steady state will be reached after 1 week of administration of the highest venetoclax dose. Ibrutinib and venetoclax PK samples will be collected at steady state on the PK days as shown at the time points listed in Table 10.

Table 10.	Pharmacokinetic Sample Schedule for Treatment-naive Open-label Arm
-----------	--

					Time Point Postdose				
Study Arm	Week	Study Day	Predose ^a	Dose ^b	1h (± 15 min)	2h (±15min)	4h (± 30 min)	6h (±30 min)	8h (±1 h)
Treatment- naive Open- label*	4	7	X	X	X	X	X	X	X
	6	1	X	X	X	X	X	X	X
	13 & beyond	(+/- 7 days)	X	X	X	X			

a Predose samples should be collected 30 minutes prior to the administration of ibrutinib and venetoclax

Refer to the laboratory binder for instructions on collecting and processing these samples. On the day of the sampling visit, the clinical staff will instruct the subject to not take a dose before arrival at the clinic. Study drug intake will be observed by clinic staff. The actual time (versus requested time) that each sample is drawn must be recorded using a 24-hour format. The same clock should be used for recording the time of dosing. In the event that medical management is needed, use of concomitant medications should be recorded. In the case of ibrutinib or venetoclax dose holds or modifications prior to the above time points, please consult with medical monitor to determine the most appropriate time at which to obtain PK blood samples.

For subjects who must start a moderate or strong CYP3A inhibitor while on treatment with ibrutinib or venetoclax, additional PK blood samples for evaluation of ibrutinib and venetoclax exposure is requested at least one week after the initiation of the concomitant CYP3A inhibitor. PK samples will be collected at the time points described above.

b Ibrutinib and venetoclax should be dosed the same time within 30 minutes after completion of the meal.

^{*} Unscheduled PK sampling schedule based on Medical Monitor request, e.g. dose modification (at least 7 days after dose modification)

7.1.4.3 Exploratory Biomarkers

Blood samples and a buccal swab will be collected and sent to the central laboratory at selected time points specified in the Schedule of Assessments (Appendix A and Appendix B).

Approximately 20 slides of fresh or most recent dated FFPE archival tumor biopsy tissue will be collected at study entry. An optional fresh tumor biopsy may be collected at the time of disease progression. A bone marrow aspirate and a bone marrow biopsy will be collected based on Section 7.1.3.5 and Section 7.1.3.6. Tumor cells from peripheral blood, bone marrow and/or tumor tissue may be studied for genomic alterations, as well as gene and/or protein expression profiling. Non-cancer cell genes derived from the buccal swab will only be used as a control for the cancer gene mutation analysis. In addition to the markers known to be involved in MCL prognosis, inhibition of BCR signaling and BCL-2 pathways may also be explored. These efforts may identify biomarkers that could support the understanding of the disease or assist with future development of treatment options.

Bone marrow aspirate and peripheral blood samples will be stored for exploratory biomarker analysis by clonoSEQ. Samples collected in this study may be stored at a biorepository for up to 10 years (or according to local regulations) for additional research as new assays are developed for ibrutinib, venetoclax and MCL. Samples will only be used to better understand the effects ibrutinib and venetoclax in MCL; sensitivity and/or resistance to the investigational treatment regimen in this study.

The research may begin at any time during the study or the post-study storage period. Stored samples will be coded throughout the sample storage and analysis process, and will not be labeled with personal identifiers.

7.1.5 Patient-Reported Outcomes

7.1.5.1 FACT-Lym for Safety Run-in and Randomization Phase

The FACT-Lym questionnaires (Appendix I) will be administered in this study. The FACT-Lym was originally developed to assess functional status and well-being of patients with NHL (Eremenco 2004). Reliability and validity have been assessed in NHL (Webster 2005) and more recently construct validity has been supported in subjects with relapsed/refractory MCL (Carter 2008).

The FACT-Lym consists of the Functional Assessment of Chronic Illness Therapy - General (FACT-G) and a lymphoma-specific additional concerns subscale (Lym).

Responses to all items are rated on a 5-point scale ranging from 0 "not at all" to 4 "very much". The recall period is the past 7 days. The lymphoma subscale includes 15 items and scores range from 0 to 60. Two summary scores may also be calculated: the FACT-Lym total score (FACT-G plus Lym) and the FACT-Lym trial outcome index (TOI) score (physical well-being+functional

well-being+lymphoma). Higher scores represent better functional status and well-being for all subscales and summary scales.

The subscale of most interest in this study will be the Lym subscale. Carter (Carter 2008) and Cella et al. (Cella 2005) reported a minimal important change score for the Lym subscale in a relapsed/refractory MCL population range from approximately 2.9 to 5.4. Therefore, a 5-point change in the Lym subscale was selected as a conservative estimate of clinically meaningful deterioration in lymphoma symptoms. Time to complete the FACT-Lym is approximately 7 to 12 minutes. All translations not currently available will be completed according to best practice guidelines for translating PRO instruments to the local language(s) (Wild 2005).

The FACT-Lym questionnaire (Appendix I) will be administered at the beginning of the clinic visits prior to any procedures or physician interactions to prevent influencing subject perceptions. The questionnaires will be administered on Week 1 Day 1, Week 13 Day 1 (±7 days); every 4 weeks for the remainder of the first year; every 8 weeks during the second and third years; and every 12 weeks thereafter until disease progression.

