7.1.3.6 Bone Marrow Aspirate and Peripheral Blood for Minimal Residual Disease (MRD) Assessment

Minimal residual disease assessment will be performed by flow cytometry at Screening for every subject to detect a dominant clone in peripheral blood or bone marrow aspirate. MRD negativity will be assessed by flow cytometry both in the peripheral blood and the bone marrow aspirate collected at documented CR. Thereafter subjects should be followed with peripheral blood MRD analyses by flow cytometry every 12 weeks (±7 days) for the remaining first year; every 16 weeks during the second and third years; and every 24 weeks thereafter until PD. MRD-negative remission is defined as undetectable MRD at documented CR in subjects who were MRD positive at screening as assessed by flow cytometry in bone marrow (BM) aspirate and/or peripheral blood and a consecutive peripheral blood sample 12 weeks later.

If the MRD assessment is positive in bone marrow at CR, a repeat bone marrow aspirate is required 24 weeks later if the subject remains in CR to evaluate MRD status in the bone marrow.

If peripheral blood becomes positive for MRD, a bone marrow sample will not be necessary; however, equivocal cases should be discussed with the medical monitor to determine the need for repeat bone marrow testing.

MRD-positive relapse is defined as a detectable increase in disease after a MRD-negative remission, as assessed by flow cytometry of a peripheral blood or BM aspirate sample.

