14 APPENDICES

Appendix A. Schedule of Assessments – Standard Ramp-up Schedule

	Week		1			2		3	4	5	6	8	10	Week 13	Response	EOT°	RFUd	LTFUw
	Day	1	2	3	1	2	3	1	1	1	1	1 (±1 day)	1 (±1 day)	& beyonda (±7 days)	Assessment ^b (±7 days)	(±7 days)	(±14	days)
						1	Stu	ıdy Drug	Adminis	tra	tion			(
Ibrutinib 560 mg daily										Co	ntin	uous						
Venetoclax daily dose / place	ebo	2	20m	g		50r	ng	100mg	200mg			400)mg con	tinuous targ	et daily dose			
Procedure	Screening Day -28 to -1																	
Informed consent	X																	
Medical history/demographic/prior treatment	X	X																
Confirm eligibility	X	X																
Concomitant medications ^e	X	X	X	X	X	X	X	X	X	X	X	X	X	X		X		
AEsf	X	X	X	X	X	X	X	X	X	X	X	X	X	X		X		
Physical exam ^g	X	X			X			X	X	X	X	X	X	X		X		
Vital signs h	X	X	X		X	X		X	X	X	X	X	X	X		X		
ECOG	X	X						X			X			X				
ECGi	X															X		
Disease Assessment																		
CT/PET/MRI/endoscopy ⁱ	X														X		X	
Tumor tissue ^k	X														(X)			
Bone marrow biopsy ^x	X														(X)			
B-symptoms	X														X		X	
Overall response assessment ^m															X		X	
MRD Bone marrow aspirate ¹	X														(X)			
MRD assessment in blood ⁿ		X													X	X		
TLS Risk Assessment ^o	X	X	X	X	X	X	X	X	X	X	X	X	X	X				
PROp		X												X				
Medical resource utilization (MRU)		Н	ospit	aliza	tions	, em	ergency	departm				oietic gr ent perio		tor use to be	documented thro	oughout		
Biomarker Bone marrow Aspirate ^l	X														(X)			
Biomarker Peripheral Blood ^u		X													X	X	X	

	Week		1			2		3	4	5	6	8	10	Week 13	Response	EOTe	RFU ^d	LTFU
	Day	1	2	3	1	2	3	1	1	1	1	1 (±1 day)	1 (±1 day)	beyond ^a (±7 days)	Assessment ^b (±7 (±7 days) days)		(±14 days)	
			•	•			Stu	ıdy Druş	Adminis	tra	tion					•	•	
Ibrutinib 560 mg daily										C	ntir	uous						
Venetoclax daily dose / place	bo		20mg	3		50n	ng	100mg	200mg			400)mg con	tinuous targ	et daily dose			
Procedure	Screening Day -28 to -1																	
Hematology ^q	X	X			X			X	X	Х	X	X	X	X	X	X		
Blood chemistry ^r	X	X	X	X	X	X	X	X	X	X	X	X	X	X		X		
Urinalysis ^s	X															X		
Serum or Urine Pregnancy	X	X														X		
Hepatitis serologies ^t	X																	
Coagulation panel	X																	
Buccal Swab		X																
Serum β ₂ -microglobulin	X																	
PK blood sampling ^v											X							
Survival status, incl. other malignancies ^w																		X
Subsequent Anticancer Therapy																	X	X

Abbreviations:

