EOT = End-of-Treatment Visit; RFU = Response Follow-up Visit; LTFU = Long-term Follow up; PRO = patient-reported outcome;

Footnotes:

- ^a After week 13, study drug dispensing visits are scheduled every 4 weeks for one year; every 8 weeks during the 2nd and 3rd years; and every 12 weeks thereafter until treatment discontinuation.
- b Response assessment visits are scheduled on Week 13 Day 1 (±7 days); every 12 weeks for the remainder of the 1st year; every 16 weeks during the 2nd and 3rd years, and every 24 weeks thereafter until PD. In addition, response assessments can be performed as clinically indicated to confirm response or progression.
- ^c An EOT visit will occur 30 days (±7) from the last dose of study drug or prior to the start of a new anticancer treatment.
- d Subjects who discontinue for reasons other than PD will have follow-up response assessments (based on Week 1 Day 1 for a subject) every 12 weeks (± 14 days) from the 1st dose for the 1st year; every 16 weeks (± 14 days) during the 2nd and 3rd years; and every 24 weeks (± 14 days) thereafter until PD.
- ^e Concomitant medications are collected from 30 days before the first dose through the 30 days after the last dose of study drug.
- f See Section 11 for details regarding the reporting of AEs.
- g A complete physical examination (at Screening and EOT) will include, at a minimum, the general appearance of the subject, height (may use prior height measurement if available in source documents) and weight, and examination of the skin, eyes, ears, nose, throat, lungs, heart, abdomen, extremities, musculoskeletal system, lymphatic system, and nervous system. At other timepoints, a limited symptom-directed physical exam will be performed. The physical exam should include an eye-related symptom assessment.
- h Vital signs (blood pressure, heart rate, and body temperature) will be assessed after the subject has rested in the sitting position for ≥ 3 minutes.
- ⁱA single 12-lead ECG will be done at Screening and at the EOT visit. Subjects should be in a supine position and resting for at least 10 minutes before obtaining the ECG. During the treatment period, ECG's may be performed at the investigator's discretion, particularly in subjects with arrhythmic symptoms (eg, palpitations, lightheadedness) or new onset dyspnea.

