- ^j CT and PET or PET/CT: A CT scan (with contrast unless contraindicated) of the neck, chest, abdomen, and pelvis and any other disease sites (eg, extremity) and a PET or PET/CT scan (CT should be of diagnostic quality) are required for the pretreatment tumor assessment within 28 days of the first dose. Thereafter, CT scans will be done for tumor assessments on Week 13 Day 1 (±7 days); every 12 weeks for the remainder of the 1st year; every 16 weeks during the 2nd and 3rd years; and every 24 weeks thereafter until PD. PET or PET/CT is mandatory to confirm a CR. For MRI refer to Section 7.1.3.2.
- ^k A total of up to 20 slides of fresh or the most recent dated FFPE archival tumor biopsy tissue will be required at study entry. An optional tumor biopsy should be collected at the time of disease progression if feasible.
- A unilateral bone marrow aspirate will be done at Screening or up to 28 days before the 1st administration of study drug for MRD testing. A 2nd bone marrow aspirate will be performed in all subjects who achieve a CR. Subsequent bone marrow aspirates will be obtained as needed (ie, if MRD in BM at CR was positive, and subject remains CR) to confirm MRD-negative CR.
- m Response assessments will be completed by the investigator using the Revised Response Criteria for Malignant Lymphoma (Cheson 2014).
- ⁿ Blood will be drawn for MRD assessments at baseline, at documented complete response and onwards every 12 weeks (±7 days) for the remainder of the 1st year; every 16 weeks during the 2nd and 3rd years; and every 24 weeks thereafter until PD.

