Time to next treatment (TTNT)	Time from the date of randomization to the date of the initiation of subsequent anti-cancer treatment. Post-treatment stem cell transplantation, CAR T-cell therapy, or other cellular therapies are not considered subsequent anti-cancer treatments for subjects responding to the treatment (CR or PR). Subjects without the use of subsequent anti-cancer treatment will be censored at the last follow-up date for subsequent anti-cancer therapy.	Method is the same as for the PFS analysis	
Time to worsening in FACT- Lym subscale ^{5,6}	Time from the date of randomization to the start date of worsening (defined by a ≥5 points reduction from baseline) in the Lym Subscale or death due to any cause, whichever occurs first.	Method is the same as for the PFS analysis	
	Subjects who have not met the definition of worsening will be censored at the last non-missing post-baseline PRO assessment. Subjects without baseline or post-baseline assessment will be censored at the date of randomization.		

Page 27 of 35

Efficacy Endpoint	Definition	Analysis Method			
	Exploratory Endpoints				
Progression- free Survival Based on Investigator Assessment after Initiation of Subsequent Anti-cancer Therapy (PFS2)	Time from the date of randomization to the date of the earliest of the following three types of events: • PD per investigator response assessment after administration of the first subsequent anticancer therapy • Death at any time on study • Initiation of the second subsequent anticancer therapy Subjects who did not experience a PFS2 event will be censored at the last adequate response assessment or the last follow-up for subsequent anti-cancer therapy (if they no longer have response assessments).	No inferential test will be conducted. For each treatment arm, the KM estimate of the median PFS2 (mPFS2) and the KM estimates at selected landmark points will be calculated using the same methods as for the primary PFS analysis.			

CMH: Cochran-Mantel-Haenszel; CI: confidence interval; CR: complete response; HR: estimate hazard ratio; ORR: overall response rate; OS: overall survival; PD: progressive disease; PFS: progression-free survival; PR: partial response.

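### The text runs questionnaires and MRD blood until progression, but the visit grids provide neither in response follow-up after treatment stops without progression

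*Protocol*

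**What the plan says.** **Text and footnotes.** Protocol 7.1.5.1 gives FACT-Lym at Week 1 and Week 13, every 4 weeks for the rest of year 1, then "every 8 weeks during the second and third years; and every 12 weeks thereafter until disease progression". Section 7.1.5.2 puts EQ-5D-5L on the same schedule. Section 7.1.3.6 follows subjects after documented CR with peripheral blood MRD every 12 weeks in year 1, then "every 16 weeks during the second and third years; and every 24 weeks thereafter until PD". Appendix A footnote p repeats the questionnaire rule. Footnote n repeats the MRD rule: "Blood will be drawn for MRD assessments at baseline, at documented complete response and onwards every 12 weeks", and so on until PD.

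**Grid and visit lists.** In Appendix A the PRO row is marked only at Week 1 Day 1 and in the column for Week 13 and beyond. Footnote a describes that column as drug-dispensing visits, ending "every 12 weeks thereafter until treatment discontinuation". The row "MRD assessment in blood" is marked at Week 1 Day 1, Response Assessment and EOT, and is blank at RFU. The row "Biomarker Peripheral Blood" is marked at all of these and also at RFU. Section 8.2.3 (EOT) lists MRD blood and no questionnaire; Section 8.3.1 (response follow-up) names neither. Appendix B has the same pattern, with EQ-5D-5L as its only questionnaire.

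**Who goes to RFU.** Footnote d: "Subjects who discontinue for reasons other than PD will have follow-up response assessments", at 12-, 16- and 24-week intervals until PD.

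**Endpoints affected.** In SAP 4.2, for time to worsening: "Subjects who have not met the definition of worsening will be censored at the last" non-missing post-baseline questionnaire. MRD-negative remission needs confirmation in peripheral blood at least 12 weeks after the negative result at CR.

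**The concern.** A subject who stops both drugs for toxicity without progression still attends RFU visits for imaging, B-symptoms, response and biomarker blood. On the grid, that subject completes no further questionnaires and, after EOT, gives no further MRD blood. Sites can reasonably follow either the footnotes or the tick marks, so practice may differ between sites.

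Two listed secondary endpoints of the Randomization Phase depend on these data. Time to worsening would be censored at the last on-treatment questionnaire, so censoring would depend on tolerability, which may differ between a two-drug arm and a one-drug-plus-placebo arm. SAP 4.2 analyses this endpoint by the PFS method, and SAP 4.1 handles treatment discontinuation for PFS by a treatment policy strategy. That cannot be carried over if nothing is measured after discontinuation, and SAP 4.2 lists no sensitivity analysis for this endpoint.

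For MRD, the SAP denominator is CR subjects who were MRD-positive at baseline and have baseline and post-baseline samples. A subject who is negative at CR and has no later sample can stay in the denominator without being able to qualify.

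**Working it through.** The plan states no figure to reproduce. The check sets the grid against the text and then works out what is lost.

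**1. Grid against text (Appendix A).** The rows align with the 18 column heads from Screening to long-term follow-up.

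| Row | Marked at | EOT | RFU | Text and footnotes |
|---|---|---|---|---|
| PRO | Week 1 Day 1; Week 13 and beyond | blank | blank | until progression |
| MRD blood | Week 1 Day 1; Response Assessment; EOT | marked | blank | until PD |
| Biomarker blood | Week 1 Day 1; Response Assessment; EOT; RFU | marked | marked | until PD |
| CT/PET/MRI/endoscopy | Screening; Response Assessment; RFU | blank | marked | until PD |

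**2. Assessments required by the text but not by the grid.** Under 7.1.5.1 questionnaires fall at Weeks 13, 17, 21, ..., 49, then 57, 65, ... . Under 7.1.3.6 MRD blood falls at Weeks 13, 25, 37, 49, then 65, 81, 97, ... once CR is documented; RFU visits fall in the same weeks. The stop and PD weeks below are assumptions.

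| Stop | PD | Questionnaires lost | MRD draws lost (CR already documented; EOT draw is extra) |
|---|---|---|---|
| Week 13 | Week 49 | 9 (17 to 49) | 3 (25, 37, 49) |
| Week 25 | Week 61 | 7 (29 to 49, 57) | 2 (37, 49) |
| Week 25 | Week 101 | 12 (29 to 49, 57 to 97) | 5 (37, 49, 65, 81, 97) |

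Questionnaires at RFU visits alone would give back 3 of 9, 2 of 7 and 5 of 12, plus one at EOT.

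**3. Who loses MRD confirmation.** Let D be the days from documented CR to the last dose. EOT falls 30 ± 7 days after the last dose (footnote c). The EOT draw can confirm if D + 30 ≥ 84, so D ≥ 84 − 30 = 54 days, or 7.7 weeks. With the window, the limit runs from 84 − 37 = 47 days to 84 − 23 = 61 days (6.7 to 8.7 weeks). Only subjects who stop all treatment within about 8 weeks of CR are exposed. If EOT is brought forward because new anticancer treatment starts, the limit is longer. The SAP then excludes samples taken after that treatment begins, so an RFU draw would help only before it starts.

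**4. Can the effect on time to worsening be sized?** Illustration with assumed inputs, none from the documents: median time to worsening on treatment 12 months in both arms, exponential times, 24-month horizon, no PD or death, and non-PD stops by 12 months of 20% (combination) and 10% (control). The hazard ratio is taken as the ratio of events per person-time. The analysis censored at the stop gives 1.00 throughout. With full follow-up it is:

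| Worsening hazard after the stop, relative to on treatment | Hazard ratio with full follow-up |
|---|---|
| 0.5 | 0.95 |
| 1 | 1.00 |
| 2 | 1.05 |
| 3 | 1.08 |

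The sign of the difference is set by the assumed post-stop hazard. The number of worsenings missed per 130 subjects is also assumption-driven: at multipliers 2 to 3 it is about 21 to 23 against 10 to 12 without PD. Adding PD at the planning medians of 23 and 14 months (Protocol 10.3) lowers it to about 14 to 16 against 6 to 7.

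**The case against.** **A reader might infer that both measures stop when treatment stops.** The documents do not support that. MRD blood is marked at EOT in the grid and listed in 8.2.3, so it ends after EOT, and that draw protects confirmation for most stops (step 3). Nor is stopping the only reading. Footnotes n and p belong to the same schedule and run to progression. Footnote b runs response assessments until PD. Section 8.2.1.7 refers sites to 7.1.5 for all questionnaire times. This stands: the schedule contradicts itself, and an early stop is what a site would do if it followed the grid. It does not dispose of the point, because footnote d sends off-treatment subjects to RFU visits whose column has neither tick.

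**A reader might also infer that the gap hides harm of the combination.** The documents give no discontinuation rates and no worsening rates after stopping. Step 4 shows the direction reversing when symptoms are assumed to ease off drug. Death from any cause counts as a worsening event under SAP 4.2, and the illustration leaves it out.

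**The trigger is narrow.** Under Protocol 5.4 a subject who stops one drug for tolerability may continue on the other, so on-treatment visits go on. The planned end of venetoclax or placebo at 104 weeks is not a trigger either, since ibrutinib continues. This stands.

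**The endpoints are not in the hierarchy.** SAP 1.6.1 tests PFS, CR rate, time to next treatment, OS and ORR. Type I error and those results are unaffected. This stands and limits the weight of the point.

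**Conclusion.** The inconsistency is real and present in both appendices: text and footnotes require questionnaires and MRD blood until progression, while the grids and Sections 8.2.3 and 8.3.1 give no questionnaire at EOT or RFU and no MRD blood at RFU.

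If sites follow the grid, questionnaires end when all study treatment stops without PD, with 7 to 12 visits lost in the illustrated cases. Time to worsening could then be informatively censored; its direction and size cannot be determined from the documents. For MRD the exposure is limited to CR subjects who stop both drugs within about 8 weeks of CR (47 to 61 days with the visit window).

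This is worth correcting because two listed secondary endpoints rest on these data. It does not touch the primary endpoint or the alpha-controlled tests.

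**What to change.** **Protocol.** Reconcile both grids and Sections 8.2.3 and 8.3.1 with the until-progression rule:
- Mark PRO at EOT and RFU (FACT-Lym and EQ-5D-5L in Appendix A, EQ-5D-5L in Appendix B).
- Mark MRD blood at RFU for subjects in CR, in both appendices. The RFU intervals already match those in 7.1.3.6.
- State the off-treatment questionnaire interval. Either it follows RFU (every 12, 16 and 24 weeks), or questionnaires are also collected between visits to keep the 4-, 8- and 12-week interval of 7.1.5.1. RFU ticks alone do not restore that interval.

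**SAP.** Report by arm the number of subjects whose FACT-Lym follow-up ended at treatment discontinuation without PD. This needs no new data and is informative even if collection can no longer be changed.

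**Cost.** One questionnaire of 7 to 12 minutes for FACT-Lym (Protocol 7.1.5.1), plus EQ-5D-5L, and one tube at visits that already take place, where biomarker blood is already drawn. If only RFU visits are used, off-treatment questionnaires are sparser than on-treatment ones, so worsening is detected later after a stop; the SAP should acknowledge this. The change needs a protocol amendment, with ethics approval before it takes effect at each site (Protocol 12.14).
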